#### **6.2.1.2.2. Supplemental Analysis**

The main analysis will also be performed on the mITT population if there is a difference of more than 10% between the evaluable and mITT populations.

#### **6.2.1.3. hSBA Titer for Each of the MenACWY Test Strains, Group 1 (0- and 12-Month Schedule)**

##### **6.2.1.3.1. Main Analysis**

- Estimand strategy: Hypothetical.
- Analysis set: Post-Vaccination 2 evaluable population for Group 1.
- Analysis methodology: Exact 2-sided 95% CIs for the percentages using the Clopper-Pearson method.
- Intercurrent events and missing data: Missing serology results will not be imputed. Participants will be summarized according to the vaccine group to which they were randomized.
- The percentage of participants in Group 1 with hSBA titers  $\geq$  LLOQ for each of the ACWY test strains at 12 and 24 months after the second dose of MenABCWY will be summarized using the post-Vaccination 2 evaluable population.

##### **6.2.1.3.2. Supplemental Analysis**

The main analysis will also be performed on the mITT population if there is a difference of more than 10% between the evaluable and mITT populations.

### **6.3. Exploratory Endpoints**

#### **6.3.1. Exploratory Immunogenicity Endpoints**

##### **6.3.1.1. hSBA Titer for Each of the Primary MenB Test Strains (A22, A56, B24, and B44)**

###### **6.3.1.1.1. Main Analysis**

- Estimand strategy: Hypothetical.
- Analysis set: Post-Vaccination 2 evaluable populations for Groups 1 and 2.
- Analysis methodology: Exact 2-sided 95% CIs for the percentages using the Clopper-Pearson method.

- Intercurrent events and missing data: Missing serology results will not be imputed. Participants will be summarized according to the vaccine group to which they were randomized.
- The percentage of participants with hSBA titers  $\geq 1:4$ ,  $\geq 1:8$ ,  $\geq 1:16$ ,  $\geq 1:32$ ,  $\geq 1:64$ , and  $\geq 1:128$  for each of the 4 primary MenB test strains at baseline and 1 month after the second dose of MenABCWY for each group, separately. The percentage of participants with hSBA titers  $\geq 1:8$ ,  $\geq 1:16$ ,  $\geq 1:32$ ,  $\geq 1:64$ , and  $\geq 1:128$  may not be reported out.
- MenB hSBA GMTs for each of the 4 primary MenB test strains at baseline and 1 month after the second dose of MenABCWY for Groups 1 and 2, separately.
- The percentage of participants achieving an hSBA titer  $\geq$  LLOQ (1:16 for A22 and 1:8 for A56, B24, and B44) for all primary MenB test strains combined (composite response) at baseline and 1 month after the second dose of MenABCWY for each group, separately.
- The percentage of participants achieving an hSBA titer  $\geq$  LLOQ for each of the 4 primary MenB test strains at 13 months after the first dose of MenABCWY in Group 2.
- The percentage of participants achieving at least a 4-fold rise in hSBA titer from baseline for each of the 4 primary MenB test strains at 1 month after the second dose of MenABCWY for each group, separately.
  - For participants with a baseline hSBA titer below the LOD (or an hSBA titer of  $< 1:4$ ), a 4-fold response is defined as an hSBA titer of  $\geq 1:16$ .
  - For participants with a baseline hSBA titer of  $\geq$  LOD (ie, hSBA titer of  $\geq 1:4$ ) and  $<$  LLOQ, a 4-fold response is defined as an hSBA titer of  $\geq 4$  times the LLOQ.
  - For participants with a baseline hSBA titer of  $\geq$  LLOQ, a 4-fold response is defined as an hSBA titer of  $\geq 4$  times the baseline titer.

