#### 4. ANALYSIS SETS (POPULATIONS FOR ANALYSIS)

Data for all participants will be assessed to determine if participants meet the criteria for inclusion in each analysis population prior to unblinding and releasing the database and classifications will be documented per standard operating procedures.

Population	Description
Enrolled	All participants who sign the ICD.
Randomly assigned to study intervention (as-randomized), also termed intent-to-treat (ITT) population	All participants who are assigned a randomization number in the IRT system.
Evaluable	Defined according to post-Vaccination 1 evaluable and post-Vaccination 2 evaluable criteria.
Modified intent-to-treat (mITT)	Defined according to post-Vaccination 1 and post-Vaccination 2 criteria.
Safety	All randomized participants who receive at least 1 dose of the study intervention and have safety data reported after vaccination. Participants will be analyzed according to the vaccine they actually received.

Defined Population for Analysis	Description
Post-Vaccination 1 evaluable population	
 
1. All randomized participants.
 
2. Eligible throughout Visit 2.
 
3. Received the study intervention at Visit 1 as randomized.
 
4. Had blood drawn for assay testing within the required time frames at Month 0 (Visit 1; before Vaccination 1) and Month 1 (Visit 2; 1 month after the first vaccination: window 28-42 days).
 
5. Had at least 1 valid and determinate MenA/C/W/Y assay result at Visit 2.
 
6. Had received no prohibited vaccines or treatment through Visit 2.
 
7. Had no important protocol deviations through Visit 2.
 

Post-Vaccination 2 evaluable population	
 
1. All randomized participants.
 
2. Eligible throughout 1 month after the second dose of MenABCWY.
 
3. Received the study intervention at Visit 1 (for Groups 1 and 2) and Visit 4 (for Group 1) and Visit 9 (for Group 2) as randomized.
 
4. Had blood drawn for assay testing within the required time frames at Month 0 (Visit 1; before Vaccination 1) and at 1 month after the second MenABCWY vaccination (Visit 5 for Group 1 and Visit 10 for Group 2: window 28-42 days).
 

Defined Population for Analysis	Description

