	
5. Had at least 1 valid and determinate MenA/C/W/Y or MenB assay result at 1 month after the second MenABCWY vaccination (Visit 5 for Group 1 and Visit 10 for Group 2).
 
6. Had received no prohibited vaccines or treatment through Visit 5 (Group 1) or Visit 10 (Group 2).
 
7. Had no important protocol deviations through Visit 5 (Group 1) or Visit 10 (Group 2).

Post-Vaccination 1 mITT population	All participants who received at least 1 study vaccination and had at least 1 valid and determinate MenB or MenA/C/W/Y assay result available at any time point from Visit 1 to Visit 2.
Post-Vaccination 2 mITT population	All participants who received at least 1 study vaccination and had at least 1 valid and determinate MenB or MenA/C/W/Y assay result available at any time point from Visit 1 to Visit 5 for Group 1 and from Visit 1 to Visit 10 for Group 2.
Vaccination 1 safety population	This population will include participants who received the first dose of study intervention at Visit 1 and for whom safety information from Visit 1 up to Visit 4 is available in Groups 1 and 2.
Vaccination 2 safety population	This population will include participants who received the second dose of study intervention at Visit 4 (MenABCWY for Group 1, saline for Group 2) and for whom safety information from Visit 4 up to Visit 7 (for Group 1) or Visit 9 (for Group 2) is available.
Vaccination 3 safety population	This population will include participants who received the third dose of study intervention at Visit 9 (MenABCWY for Group 2) and for whom safety information from Visit 9 through Visit 10 is available.
Follow-up safety population 1	This population will include participants who received the first dose of study intervention and for whom safety information from Visit 2 up to Visit 4 in Groups 1 and 2 is available.
Follow-up safety population 2	This population will include participants who received the second dose of study intervention (MenABCWY for Group 1, saline for Group 2) and for whom safety information from Visit 5 up to Visit 7 (for Group 1) or Visit 9 (for Group 2) is available.

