For determination of the evaluable population(s), items 1 through 5 will be computerized checks of the data, while items 6 and 7 will be determined by clinical review. An important protocol deviation is a protocol deviation that, in the opinion of the sponsor's global medical monitor, would materially affect assessment of immunogenicity, eg, participant receipt of a prohibited vaccine or medication that might affect immune response or a medication error with suspected decrease in potency of the vaccine. The global medical monitor from the sponsor will identify those participants with a protocol deviation prior to unblinding of the study.

For participants withdrawn early, they will be included in the respective follow-up population, in case they have any type of AEs in the respective AE follow-up intervals.

For Analysis 1 (per [Section 7.1](#)), the post-Vaccination 1 evaluable population will be fully defined for both Groups 1 and 2. Similarly, the post-Vaccination 2 evaluable population will be fully defined for Group 1 for Analysis 1. The final determination of the protocol

deviations, and hence the post-Vaccination 2 evaluable population for Group 2, will be completed for the final analysis.

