**6.3.1.2. hSBA Titer for Each of the MenACWY Test Strains (After Vaccination 1)****6.3.1.2.1. Main Analysis**

- Estimand strategy: Hypothetical.
- Analysis set: Post-Vaccination 1 evaluable populations for Groups 1 and 2.
- Analysis methodology: Exact 2-sided 95% CIs for the percentages using the Clopper-Pearson method.
- Intercurrent events and missing data: Missing serology results will not be imputed. Participants will be summarized according to the vaccine group to which they were randomized.
- hSBA GMTs for each ACWY test strain at baseline and 1 month after the first dose of MenABCWY for each group, separately and combined, may be summarized.
- The percentage of participants with hSBA titers  $\geq$  LLOQ for each ACWY test strain at 13 months after the first dose of MenABCWY (Group 2 only).
- The percentage of participants achieving at least a 4-fold rise in hSBA titer from baseline for each ACWY test strain at 1 month after the first dose of MenABCWY for each group, separately and combined, may be summarized.
  - For participants with a baseline hSBA titer below the LOD (or an hSBA titer of  $< 1:4$ ), a 4-fold response is defined as an hSBA titer of  $\geq 1:16$ .
  - For participants with a baseline hSBA titer of  $\geq$  LOD (ie, hSBA titer of  $\geq 1:4$ ) and  $<$  LLOQ (ie, an hSBA titer of 1:8), a 4-fold response is defined as an hSBA titer of  $\geq 4$  times the LLOQ.
  - For participants with a baseline hSBA titer of  $\geq$  LLOQ, a 4-fold response is defined as an hSBA titer of  $\geq 4$  times the baseline titer.

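### The exploratory Group 2 MenB percentage at Month 13 uses an analysis set that depends on Months 36 and 37, so its main analysis drops valid one-dose results for later events (minor).

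*SAP*

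**What the plan says.** SAP 6.3.1.1.1 names one analysis set for all its MenB exploratory summaries, the post-Vaccination 2 evaluable populations. Among them, without exception, is the Group 2 percentage at or above the LLOQ "for each of the 4 primary MenB test strains at 13 months after the first dose of MenABCWY in Group 2". That sample is drawn at Visit 5, one month after the saline injection, when Group 2 has had one dose of MenABCWY. Protocol 9.4.1 makes the same assignment. The estimand in protocol 3 and SAP 2.1.6 is written for participants who received two doses.

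SAP 4 defines the set. Study intervention must have been received at "Visit 1 (for Groups 1 and 2) and Visit 4 (for Group 1) and Visit 9 (for Group 2) as randomized". Blood must have been drawn at baseline and "at 1 month after the second MenABCWY vaccination (Visit 5 for Group 1 and Visit 10 for Group 2: window 28-42 days", with at least one valid result at that later visit. The last criterion reads "Had no important protocol deviations through Visit 5 (Group 1) or Visit 10 (Group 2", and the one on prohibited vaccines and treatments runs to the same visits.

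The ACWY percentage from the same Visit 5 draw, "for each ACWY test strain at 13 months after the first dose of MenABCWY (Group 2 only", is assigned by SAP 6.3.1.2.1 to the post-Vaccination 1 evaluable population, which has no criterion after Visit 2.

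SAP 7.1 puts Group 2 Visit 5 immunogenicity data into Analysis 1. SAP 4 completes the Group 2 post-Vaccination 2 evaluable set only for the final analysis.

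**The concern.** A result that is complete at Month 13 should not depend on dosing, bleeding or compliance at Months 36 and 37. Under the present assignment, a Group 2 participant with a valid Visit 5 titre leaves the main analysis by withdrawing later, missing the Visit 9 dose, receiving a prohibited vaccine in the third year, or being bled on day 43 after Visit 9. The main estimate is thus restricted to those retained to the end. It also cannot be read beside the ACWY percentage as a description of the same people.

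The set is strict about later events and silent about the time point being analysed. For Group 2 it lists no Visit 5 draw window, no Visit 5 result and no saline injection at Visit 4 as criteria. Deviations at those visits can be caught only at item 7, where "items 6 and 7 will be determined by clinical review".

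The item is exploratory, but SAP 2.1.6 withdraws the 13-month GMTs. This percentage is therefore the only Month 13 MenB summary that SAP 6.3.1.1.1 still lists.

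**Working it through.** **1. The plan's own figures reproduce.** Protocol 9.2 gives 150 per group and up to 20% excluded: 150 × (1 − 0.20) = 120. The Clopper-Pearson limits for x of n are L = Beta(0.025; x, n − x + 1) and U = Beta(0.975; x + 1, n − x), and the half-width is (U − L)/2. At n = 120 this gives 9.09, 8.53, 7.51 and 5.77 points for 60, 70, 80 and 90%, which round to Table 4 (9.1, 8.5, 7.5, 5.8).

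**2. The time gap.** Visit 5 is 28 to 42 days after Visit 4, Visit 9 is 700 to 756 days after Visit 4, and Visit 10 is 28 to 42 days after Visit 9 (schedule of activities).

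- Visit 5 to Visit 9: 700 − 42 = 658 to 756 − 28 = 728 days.
- Visit 5 to Visit 10: 658 + 28 = 686 to 728 + 42 = 770 days.

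**3. Group 2 criteria, side by side (SAP 4).**

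| Criterion | MenB at Month 13 (post-Vaccination 2 set) | ACWY at Month 13 (post-Vaccination 1 set) |
|---|---|---|
| Doses as randomized | Visits 1 and 9 | Visit 1 |
| Draws in window | Visits 1 and 10 | Visits 1 and 2 |
| Valid result | At least 1 at Visit 10 | At least 1 ACWY at Visit 2 |
| Prohibited treatment, important deviations | None through Visit 10 | None through Visit 2 |
| Any Visit 5 draw or result criterion | No | No |

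Neither set is built around Visit 5. The MenB set adds conditions that arise 658 to 770 days after the sample was taken.

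**4. Results dropped.** The documents do not split the 20% exclusion by time, so the number with a valid Month 13 result has to be assumed. Take 128 to 142, with 120 evaluable:

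- 128 − 120 = 8 dropped (8/128 = 6%).
- 142 − 120 = 22 dropped (22/142 = 15%).

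A wider assumption of 125 to 150 gives 5 to 30 dropped (4% to 20%).

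**5. Precision, at an assumed 50% rate.** Clopper-Pearson half-widths are 9.26 (60/120), 8.96 (64/128) and 8.50 (71/142). The widening is 9.26 − 8.96 = 0.30 to 9.26 − 8.50 = 0.76 point.

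**6. Possible shift.** Shift = share dropped × difference in response between kept and dropped participants. With an assumed 10-point difference: 8/128 × 10 = 0.6 to 22/142 × 10 = 1.5 points. If later loss is unrelated to the Month 13 response, the difference and the shift are zero.

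**7. The mITT route back.** SAP 6.3.1.1.2 runs the mITT analysis only if the evaluable and mITT populations differ by more than 10%. It gives neither the denominator nor the basis of that rule (population size or result). Read as population size with an assumed mITT of 150, 120 evaluable gives 30/150 = 20%, and the rule is met. At 135 evaluable, 15/150 = 10% does not meet it but 15/135 = 11.1% does. The number of dropped results that would return therefore cannot be bounded from the documents.

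**The case against.** The set agrees with the declared estimand. The item sits under a two-dose MenB objective, its population is participants with two doses, and protocol 9.1.1 targets the setting in which the schedule is followed. A fixed cohort seen at baseline, Month 13 and Month 37 is a legitimate display. The ACWY contrast has a structural origin: ACWY has a one-dose objective, while MenB is not assayed at Visit 2 and so has no post-dose-1 set. The protocol also plans the mITT analysis without condition.

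Much of this is fair. The SAP does not depart from the protocol here, and a fixed-cohort display may stay. But agreement between estimand and set shows only that both documents carry the mismatch. The plan does not offer the fixed cohort as its reason, and it does not treat ACWY at Month 13 that way. The mITT analysis does not change the main estimate.

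Three stronger readings are tempting, and the documents do not support them.

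- **That the Month 13 estimate is biased.** This needs later loss to be related to the Month 13 response, and nothing in the documents shows it. SAP 5.3.2 expects missing assay data to be completely at random. If the same holds for later exclusion, the cost is precision and comparability only.
- **That Analysis 1 contradicts the set definition.** No text commits to a Group 2 MenB percentage at Analysis 1, and protocol 9.5.1 promises only selected data, including Group 1 immunogenicity. The set for such a result is unspecified, which is a gap.
- **That the post-Vaccination 1 set is a ready remedy**, since at Analysis 1 "the post-Vaccination 1 evaluable population will be fully defined for both Groups 1 and 2". It requires an in-window Visit 2 draw and a Visit 2 ACWY result, so valid Month 13 MenB results would still be lost for reasons unrelated to them. Its check on prohibited treatments reads "Had received no prohibited vaccines or treatment through Visit 2", so it screens nothing between Visits 2 and 5.

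**Conclusion.** The point holds and is minor. As written in both documents, the main analysis of the Group 2 MenB percentage at Month 13 excludes valid one-dose results because of events about 24 months later, and it describes different participants from the ACWY percentage at the same draw. For Group 2, the set also has no Visit 5 draw or result criterion and is not completed by Analysis 1.

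Under the stated assumptions the loss is 8 to 22 results, the interval is about 0.3 to 0.8 point wider, and a 10-point difference between kept and dropped participants would move the estimate by about 0.6 to 1.5 points. Against a half-width of about 9 points this is small. The certain part is the definition; the sizes are illustrations.

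The scope is one exploratory, descriptive item. A reader might infer that the primary MenB percentages or the LCI-threshold comparisons are affected. They are not: for Group 2 these concern one month after the second MenABCWY dose, the visit around which the post-Vaccination 2 set is defined.

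**What to change.** Define in SAP 4 a Group 2 13-month evaluable set that ends at Visit 5:

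- randomized, and eligible through Visit 5;
- MenABCWY at Visit 1 and saline at Visit 4, as randomized;
- baseline and Visit 5 draws within their windows;
- at least one determinate result at Visit 5;
- no prohibited vaccine or treatment and no important deviation through Visit 5.

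Use this set for both the MenB and the ACWY 13-month percentages, at the final analysis and at Analysis 1 if they are reported there. Do not substitute the post-Vaccination 1 evaluable set. The post-Vaccination 2 version can stay as a supplementary fixed-cohort display.

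Align the population wording in protocol 3 and 9.4.1 and in SAP 2.1.6, 6.3.1.1.1, 6.3.1.2.1 and Appendix 1.

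The cost is one extra population flag, its clinical review through Visit 5, and the wording changes. No new samples, assays or visits are needed.

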### 6.3.1.1.2. Supplemental Analysis

The main analysis will also be performed on the mITT population if there is a difference of more than 10% between the evaluable and mITT populations.

One additional supplementary analysis without hypothesis testing will be performed to assess the lower bound of the 2-sided 95% CI for the percentage of participants achieving at least a 4-fold rise from baseline in hSBA titers for each of the 4 primary MenB test strains and composite response against the prespecified LCI thresholds at 1 month following the second dose of MenABCWY for Group 2. The LCI thresholds for a 4-fold rise from baseline and composite response for MenB are listed for reference in [Table 9](#).

**Table 9. LCI Thresholds for MenB and Composite Response**

	Strain Type	LCI Thresholds
hSBA titer fold rise $\geq 4$ from baseline	A22	75%
	A56	85%
	B24	65%
	B44	75%
Composite response (hSBA titer $\geq$ LLOQ for all 4 primary strains combined)		70%

**6.3.1.2. hSBA Titer for Each of the MenACWY Test Strains (After Vaccination 1)****6.3.1.2.1. Main Analysis**

- Estimand strategy: Hypothetical.
- Analysis set: Post-Vaccination 1 evaluable populations for Groups 1 and 2.
- Analysis methodology: Exact 2-sided 95% CIs for the percentages using the Clopper-Pearson method.
- Intercurrent events and missing data: Missing serology results will not be imputed. Participants will be summarized according to the vaccine group to which they were randomized.
- hSBA GMTs for each ACWY test strain at baseline and 1 month after the first dose of MenABCWY for each group, separately and combined, may be summarized.
- The percentage of participants with hSBA titers  $\geq$  LLOQ for each ACWY test strain at 13 months after the first dose of MenABCWY (Group 2 only).
- The percentage of participants achieving at least a 4-fold rise in hSBA titer from baseline for each ACWY test strain at 1 month after the first dose of MenABCWY for each group, separately and combined, may be summarized.
  - For participants with a baseline hSBA titer below the LOD (or an hSBA titer of  $< 1:4$ ), a 4-fold response is defined as an hSBA titer of  $\geq 1:16$ .
  - For participants with a baseline hSBA titer of  $\geq$  LOD (ie, hSBA titer of  $\geq 1:4$ ) and  $<$  LLOQ (ie, an hSBA titer of 1:8), a 4-fold response is defined as an hSBA titer of  $\geq 4$  times the LLOQ.
  - For participants with a baseline hSBA titer of  $\geq$  LLOQ, a 4-fold response is defined as an hSBA titer of  $\geq 4$  times the baseline titer.

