2.1. Study Rationale

In Study B1971057, an FIH and POC study for MenABCWY, 543 participants received MenABCWY on a 0- and 6-month schedule. Results from B1971057 indicated MenABCWY, when given on a 0- and 6-month schedule, is well tolerated with an acceptable safety profile and also provides a high degree of protective immune responses without interference among all 5 serogroup components tested. These results are comparable to Phase 2 and 3 bivalent rLP2086 studies, which demonstrate that by increasing the interval between 2 doses, immune responses are enhanced. Study B1971057 also demonstrated that 1 dose of MenACWY-TT (Nimenrix), as a component of MenABCWY, provides protective immune responses in a high proportion of those vaccinated, consistent with Phase 3 data supporting licensure of Nimenrix.

The aim of this Phase 2b descriptive study is to assess the potential utility of MenABCWY in the framework of current US meningococcal vaccination practices, which are based on ACIP recommendations. The ACIP recommends that children 11 to 12 years of age should receive a MenACWY conjugate vaccination with a booster dose at 16 years of age and that adolescents and young adults 16 to 23 years of age may be vaccinated with a 2- or 3-dose series MenB vaccine to provide short-term protection against most strains of serogroup B meningococcal disease. A single dose of MenACWY conjugate provides protection in early adolescence, but the second dose is required to extend that protection into late adolescence

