	
● hSBA GMTs for each ACWY test strain at baseline and 1 month after the second dose of MenABCWY.● The percentage of participants achieving at least a 4-fold rise in hSBA titers from baseline for each ACWY test strain at 1 month after the second dose of MenABCWY.
○ For participants with a baseline hSBA titer below the LOD (or an hSBA titer of <1:4), a 4-fold response is defined as a participant with an hSBA titer of $\geq 1:16$.○ For participants with a baseline hSBA titer of \geq LOD (ie, hSBA titer of $\geq 1:4$) and < LLOQ (ie, an hSBA titer of 1:8), a 4-fold response is defined as a participant with an hSBA titer of ≥ 4 times LLOQ.○ For participants with a baseline hSBA titer of \geq LLOQ, a 4-fold response is defined as a participant with an hSBA titer of ≥ 4 times the baseline titer.
--	---

The following analyses for the ACWY test strains are based on the post-Vaccination 1 evaluable population for Groups 1 and 2 (separately):

	
● hSBA GMTs for each ACWY test strain at baseline, 1 month after the first dose of MenABCWY, and 13 months after the first dose of MenABCWY (Group 2 only).● The percentage of participants achieving at least a 4-fold rise in hSBA titer from baseline for each ACWY test strain at 1 month after the first dose of MenABCWY.
○ For participants with a baseline hSBA titer below the LOD (or an hSBA titer of <1:4), a 4-fold response is defined as a participant with an hSBA titer of $\geq 1:16$.
--	--

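### The exploratory Group 2 ACWY percentage at Month 13 uses an analysis set whose compliance checks all end at Month 1, so a later meningococcal vaccination is not screened out

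*SAP*

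**What the plan says.** In SAP 6.3.1.2.1 one item is the Group 2 percentage with titers at or above "LLOQ for each ACWY test strain at 13 months after the first dose of MenABCWY (Group 2 only"). The set for that section is given as "Analysis set: Post-Vaccination 1 evaluable populations for Groups 1 and 2". Protocol 9.4.1 (Exploratory) agrees; the list containing this item opens with "The following analyses for the ACWY test strains are based on the post-Vaccination 1 evaluable population".

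SAP Section 4 defines the set by these criteria, among others:

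- "Eligible throughout Visit 2"
- "Received the study intervention at Visit 1 as randomized"
- "Had received no prohibited vaccines or treatment through Visit 2"
- "Had no important protocol deviations through Visit 2"

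The required blood draws are those at Visits 1 and 2. Protocol 9.3 gives the same definition.

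The Month 13 sample is the Visit 5 draw, one month after Group 2 receives saline at Visit 4 (Protocol 1.2). The stated strategy is hypothetical (SAP 6.3.1.2.1). Protocol 9.1.1 explains this as the vaccine effect if participants keep to the schedule and the protocol requirements. Nonstudy meningococcal vaccines are prohibited (Protocol 6.5.1), and their receipt is recorded until participation ends (Protocol 6.5).

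**The concern.** The set is checked to Month 1 and the outcome is measured at Month 13. Between the two lie about a year of ordinary care and a second study injection, and neither is screened for this summary. A Group 2 participant who receives a nonstudy meningococcal vaccine in that interval has already met every criterion. On the plain text, so has one who receives MenABCWY instead of saline at Visit 4. The resulting titer is then reported as what remains of one dose.

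This percentage carries some weight although it is exploratory. Visit 5 in Group 2 is the only draw that shows ACWY persistence after a single dose. Group 1 has no draw between Visit 2 and its second dose, and Group 2 has none between Visit 5 and its second dose (Protocol 1.2). The SAP has dropped the Month 13 GMTs (2.1.6 and Appendix 1), which leaves this percentage as the planned numerical ACWY summary at that time. It bears on the stated aim of learning whether one early-adolescent dose could support ACWY protection until the second (Protocol 2.1 and 4.2). Any error from added meningococcal vaccination would flatter the vaccine.

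**Working it through.** **1. Does another rule close the gap?**

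| Place | What it does | Removes the affected Visit 5 titer? |
|---|---|---|
| SAP 4, post-Vaccination 1 evaluable | Checks through Visit 2 | No |
| SAP 5.3.2 | Sets insufficient, indeterminate and not-done results to missing | No |
| SAP 4.1 | Puts recipients of an incorrect vaccine in mITT under the randomized group; silent on evaluable sets | Not clearly; does not address nonstudy vaccines |
| SAP 6.3.1.2.2 | Conditional repeat on mITT | No; mITT keeps these participants |
| Protocol 8.11.2 | Sites confirm eligibility and record nonstudy vaccines | Not an analysis exclusion |

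**2. The same blood sample under the other set.** The Group 2 MenB percentage at Month 13 uses the post-Vaccination 2 evaluable population (SAP 6.3.1.1.1). For Group 2, its prohibited-vaccine and deviation checks run through Visit 10. One participant could therefore be excluded from the MenB result and kept in the ACWY result from the same tube.

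**3. The plan's precision figures.** Protocol 9.2 assumes 150 per group and up to 20% exclusion: 150 x (1 - 0.20) = 120. The exact Clopper-Pearson half-widths at n = 120, recomputed, are 9.09, 8.53, 7.51 and 5.77 points at 60, 70, 80 and 90%. Table 4 states 9.1, 8.5, 7.5 and 5.8, so the figures reproduce.

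**4. Size of the effect.** Let p be the true one-dose proportion at or above LLOQ and q the fraction of analysed participants with an extra meningococcal vaccination before the draw. In the worst case all of those are at or above LLOQ:

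observed = (1 - q)p + q = p + q(1 - p), so shift = q(1 - p).

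The documents give neither q nor p. Assumed values give these shifts in percentage points:

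| q | p = 50% | p = 60% | p = 80% | p = 90% |
|---|---|---|---|---|
| 1% | 0.5 | 0.4 | 0.2 | 0.1 |
| 2% | 1.0 | 0.8 | 0.4 | 0.2 |
| 3% | 1.5 | 1.2 | 0.6 | 0.3 |

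In whole participants, 3 affected of 120 at p near 60% gives 73/120 = 60.8% instead of 70/117 = 59.8%, a shift of 1.0 point. At p near 90% it gives 108/120 = 90.0% instead of 105/117 = 89.7%, a shift of 0.3 points.

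**5. Against the interval.** At p = 60% the largest tabulated shift is 1.2 points against a half-width of 9.1. At p = 90% it is 0.3 against 5.8. Table 4 stops at 60%; for 61/120 the exact interval is 41.6 to 60.1, a half-width of about 9.3, against a shift of 1.5 at p = 50%.

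**The case against.** The best opposing case is that few participants will be affected, and most of it stands. Nonstudy meningococcal vaccines are prohibited, and sites review eligibility and nonstudy vaccines at Visits 3, 4 and 5. An error at Visit 4 is unlikely to pass unnoticed. Containers are assigned by IRT, and saline comes as a prefilled syringe while MenABCWY needs reconstitution. Unblinded staff prepare it, and medication errors go on the CRF. These safeguards lower q, but they do not exclude a titer from analysis.

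SAP 4.1 can also be read as placing recipients of an incorrect vaccine in mITT only. The text does not settle that, so the wrong-injection half of the point is less firm than the nonstudy-vaccine half, which SAP 4.1 does not touch.

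A reader might infer four stronger points that the documents do not support:

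- **Routine vaccination makes contamination likely.** Protocol 2.1 says that "children 11 to 12 years of age should receive a MenACWY conjugate vaccination". But every participant receives an ACWY component at Visit 1, so that dose has largely been given in the study. The next one described is a booster at 16 years. Participants are under 15 at randomization, and the latest in-window Visit 5 is 394 + 42 = 436 days after Visit 1, which is 71 days over a year. Only those randomized within about 10 weeks of turning 15 could be 16 by that draw.
- **The bias could reach 5 points.** That needs q = 10% together with p = 50%. Nothing in the documents supports 12 affected of 120.
- **Every affected titer inflates the result.** A participant already at or above LLOQ from the first dose adds nothing.
- **A Visit 5 draw outside 28 to 42 days is also contamination.** In Group 2 that window follows saline. An early or late draw only slightly changes the time since dose 1.

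**Conclusion.** The rule is wrong as written, and the severity is minor. For the Month 13 Group 2 ACWY percentage the analysis set stops checking at Visit 2, so it does not deliver the hypothetical estimand that the plan declares. This is clear for nonstudy meningococcal vaccines and holds on the plain text for MenABCWY given in error at Visit 4.

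Meningococcal vaccination can only raise responder status or leave it unchanged, so the error runs in one direction. For assumed q of 1 to 3% and p of 50 to 90% it is 0.1 to 1.5 points at worst, probably small and inside the half-width. The interval would not reflect it. The range rests entirely on assumed q and p.

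A reader might take this as a threat to the trial's main results, and it is not. The endpoint is exploratory and the study tests no hypotheses. The lower-limit thresholds in SAP Tables 9 and 10 apply only after the second dose.

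**What to change.** In SAP 6.3.1.2.1, for the Month 13 Group 2 ACWY summary only, restrict to post-Vaccination 1 evaluable participants who also

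1. received saline at Visit 4 as randomized, and
2. had no prohibited vaccine or treatment and no important protocol deviation through the Visit 5 draw.

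Set other Month 13 titers to missing for this summary. Do not add a 28-to-42-day window after saline.

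Moving the summary to the post-Vaccination 2 evaluable set would be a poorer remedy. For Group 2 that set requires the Visit 9 dose and the Visit 10 sample, and its injection item does not name the Visit 4 saline. It is final only at the final analysis, while Visit 5 data enter Analysis 1 (SAP 4 and 7.1).

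The cost is one sentence, one derived flag, and clinical review of Group 2 deviations through Visit 5 in time for Analysis 1. Dosing details and nonstudy meningococcal vaccine dates are already collected (Protocol 6.1.1 and 6.5). The endpoint is exploratory, and both documents call for a protocol amendment only for major changes to primary endpoints or their analysis (Protocol 9, SAP 2). The downside is a few fewer participants at Month 13. The documents do not say whether Analysis 1 has been run; if it has, label the restricted result as added later and show it beside the planned one.
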